4.7.3.8 European Quality of Life 5-Dimension Questionnaire, 3-Level Version

The EuroQol 5-dimension questionnaire (EQ-5D) is a generic HRQoL measure used to generate a utility score for use in health economic modeling. This self-reported questionnaire consists of two pages comprising the EQ-5D descriptive system and the EuroQol visual analogue scale (EQ VAS). The EQ-5D-3L descriptive system includes

Rituximab—F. Hoffmann-La Roche Ltd
27/Statistical Analysis Plan WA29330

three response options for each domain ranging from “no problems” to “extreme problems.” The EQ-5D-3L comprises 5 dimensions of health on the following domains:

- Mobility
- Self-care
- Usual activities
- Pain/discomfort
- Anxiety/depression

The EQ VAS records the respondent’s self-rated health status on a vertical graduated (0–100) visual analogue scale. The EQ-5D-3L will be converted to a single index utility score as per the EQ-5D-3L user guide (Version 4.0, [Appendix 9](#)).

Absolute values and change from baseline up to Week 52 in EQ-5D-3L single index utility score and the EQ VAS will be analyzed using summary statistics. Plots may also be produced.

Additional post hoc analysis may be done, depending on requirements for economic modelling.

Missing data will be handled as per the EQ-5D-3L user guide. Rescue data will be set to missing from the point of rescue onwards, no imputation will be made for rescue data.

4.7.3.9 Skindex-29

The Skindex-29 is a HRQoL measure evaluating the impact of patients’ dermatologic condition over the previous 4 weeks. The Skindex-29 consists of 30 questions on a 5-point Likert-type scale ranging from “Never” to “All the time” and comprises the following four domains:

- Emotions
- Symptoms
- Functioning
- Treatment

The single item asking about treatment is not scored. All other responses will be transformed to a linear scale (0–100), with higher scores indicating higher impact of skin disease. Scores will be calculated per the Skindex Manual (Version 2.0 or later; [Appendix 10](#)).

The mean and change from baseline global score will be summarized by visit and treatment group. Plots may also be produced.

Rituximab—F. Hoffmann-La Roche Ltd
28/Statistical Analysis Plan WA29330

The overall (global) score will be set to missing if more than 25% of the responses are missing. Data for patients who rescue will be set to missing from the point of rescue onwards, no imputation will be made for rescue data.

4.7.3.10 Disease Control

The number and percentage of patients in a state of disease control will be summarized by visit up to Week 52. Patients who receive rescue therapy will be considered as not in control from the point of rescue onwards, regardless of the recorded value on the eCRF.

4.7.4 Subgroup Analyses

The proportion of patients achieving complete and partial remission by Week 24 and Week 52, and sustained complete remission by Week 52 will be summarized descriptively for the following subgroups (summaries will only be carried out for subgroups where there is a minimum of 20% of patients from the overall population):

- Gender (male, female)
- Age (≤ 50 years, > 50 years)
- Region (North America, Rest of World)
- Duration of illness (0 to ≤ 1 years, > 1 to 2 years)
- Baseline prednisone dose (60 or 80 mg/day by Day 1)
- Site of disease (mucosal only, mucocutaneous, cutaneous only)
- Baseline PDAI^a score (quartiles)

Additional descriptive analyses for subgroups may be carried out, as required.

4.8 PHARMACOKINETIC AND PHARMACODYNAMIC ANALYSES

Serum rituximab concentrations will be listed by patient and nominal time of collection. Summary statistics of serum rituximab concentrations will be presented by nominal time of collection including n, mean, SD, coefficient of variation, geometric mean, median, and range.

Individual and mean serum rituximab concentration versus time profiles will be plotted on both linear and logarithmic scales.

A population PK analysis will be conducted to estimate the typical PK parameter values and to characterize the between-patient variability of those parameters. The effect of several physiological covariates on between-patient variability will also be studied in this patient population.

Exploratory graphical and statistical techniques, including linear, nonlinear, and logistic regression, faceted group comparison plots, etc., will be used to explore potential relationships between treatment groups, and markers of rituximab exposure, safety,

Rituximab—F. Hoffmann-La Roche Ltd
29/Statistical Analysis Plan WA29330

and/or efficacy (e.g., peripheral CD19+ B-cell counts, ADA, and autoantibody concentrations).

Depending on the number of PK samples available from this study where the investigation of rituximab PK is an exploratory objective, the data may be pooled with data from previous studies. Once the data is available and reviewed, a separate PK analysis plan may be drafted, if appropriate.

Full methodology will be documented with the final results of the analyses in a separate report.

4.9 SAFETY ANALYSES

The safety analysis will be performed on the safety population as defined in Section 4.1.3. Analyses of safety data up to Week 52 will include rescue patients up to the point of rescue only. Post-rescue data for patients who receive rescue therapy will be summarized separately for selected key safety outputs.

4.9.1 Exposure to Study Medication

The number and percentage of patients who received RTX will be summarized by treatment course, along with summary statistics for the dose of RTX received at each infusion and overall.

Duration of rituximab exposure will be calculated as:

- exposure date – date of first rituximab infusion + 1 where exposure date is the earliest of the following:
 - Week 52 visit (using upper visit window of Day 364+10 days)
 - Date of early withdrawal

RTX exposure data will be determined using the dosing information as recorded on the RTX administration log on the eCRF and the actual treatment received as per IxRS. Exposure to RTX will not include RTX given as rescue, which will be analyzed separately.

MMF exposure data will be determined using the dosing information as recorded on the MMF administration log on the eCRF and the actual treatment received as per IxRS.

Exposure to MMF will be calculated as:

- date of the last MMF administration – date of the first MMF administration + 1

Exposure to MMF will not include MMF given as rescue, which will be analyzed separately.

The total cumulative dose will be calculated by summing the total daily dose over the treatment duration. Average daily dose will be calculated as:

- total cumulative dose ÷ treatment duration

Rituximab—F. Hoffmann-La Roche Ltd
30/Statistical Analysis Plan WA29330

4.9.2 Adverse Events

Adverse events will be mapped and reported using the Medical Dictionary for Regulatory Activities (MedDRA) thesaurus using the most current version at the time of analysis (version 17.1 or later). Glossaries showing the mapping of investigator verbatim terms to coded events will be produced.

A listing of AEs occurring during screening (prior to Day 1) will be produced to capture AEs occurring during the oral corticosteroid taper.

Treatment-emergent AEs (TEAEs) will be summarized. All AEs referenced in the section below will be TEAEs. TEAEs are defined as those AEs with observed or imputed onset date on or after the start date of trial treatment. Only where the most extreme intensity is greater than the initial intensity (or if most extreme intensity is not missing and initial intensity is missing) will events with an onset date prior to the start of trial treatment be considered treatment-emergent. An AE with a completely missing start date will be assumed to be treatment-emergent unless the AE has a complete non-imputed end date that is prior to study Day 1.

Listings will show all AEs reported, including AEs occurring after rescue therapy, and any AEs that may have occurred during the oral corticosteroid dose adjustments in the screening period.

AEs will be summarized by system organ class (SOC) and preferred term (PT), and will be presented in order of descending frequency summed across the treatment arms within each SOC and PT.

The following will be summarized, and/or listings produced where required:

- AEs
- Serious Adverse Events (SAEs)
- AEs by relationship to study medication
- AEs leading to study drug dose modification or interruption
- AEs by common terminology criteria grade
- Infections
- Serious Infections
- Corticosteroid-related AEs
- Infusion related reactions (IRRs) (Roche Standard AE Grouped Term [AEGT] MedDRA Basket)
- Serious IRRs
- AEs leading to withdrawal

Rituximab—F. Hoffmann-La Roche Ltd
31/Statistical Analysis Plan WA29330

- AEs leading to death
- Opportunistic infections (OI) , including serious OI (Roche Standard AE Grouped Term [AEGT] MedDRA Basket for Opportunistic Infections)

If an imbalance in exposure is found between treatment groups, AE rates per 100 patient-years exposure may be calculated. AE rate per 100 patient-years is defined as:

$$(\text{number of events} \div \text{total exposure}) \times 100$$

The 95% CIs will be calculated based on exact X^2 distribution.

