5.3.1 Adverse Event Reporting Period

Investigators will seek information on adverse events at each patient contact. All adverse events, whether reported by the patient or noted by study personnel, will be recorded in the patient's medical record and on the Adverse Event eCRF.

Rituximab—F. Hoffmann-La Roche Ltd
68/Protocol WA29330, Version 5

After informed consent has been obtained but prior to initiation of study drug, only serious adverse events caused by a protocol-mandated intervention (e.g., invasive procedures such as biopsies, discontinuation of medications) should be reported (see Section 5.4.2 for instructions for reporting serious adverse events). In addition, any adverse events occurring during any corticosteroid dose adjustment during the screening period should be reported.

After initiation of study drug, all adverse events, regardless of relationship to study drug, including corticosteroid-related adverse events, will be reported during the treatment period. During the SFU period, serious adverse events and all infectious adverse events, irrespective of causality, will be reported. After this period, the investigator is not required to actively monitor patients for adverse events; however, the Sponsor should be notified if the investigator becomes aware of any post-study serious adverse events (see Section 5.6).

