Appendix 11 Imputation Rules for Partial or Missing Dates (cont.)

	Start Date/Time	End Date/Time
Laboratory	Partially Missing Day: No imputation Month: No imputation Year: No imputation Seconds: 23 Minutes: 59 Hours: 59 Completely Missing Date: No imputation Time: 23:59:59	Partially Missing Day: No imputation Month: No imputation Year: No imputation Seconds: 23 Minutes: 59 Hours: 59 Completely Missing Date: No imputation Time: 23:59:59
Adverse Events	Partially Missing Day: If the MM-YYYY of start date is not equal to the MM-YYYY of first treatment date then set to 01-MM-YYYY. If the MM-YYYY of start date is equal to the MM-YYYY of first treatment date then if the end date is \geq date of first treatment set to max(01-MM-YYYY, date of first treatment) , otherwise if end date < date of first treatment set to 01-MM-YYYY. Month: Set to max(01-01-YYYY, date of first treatment). Year: Set to start date of first treatment. Seconds: 59 Minutes: 59 Hours: 23 Completely Missing Set to start date of first treatment. Note: For all imputations above, if the resulting imputed start date is after the end date then set start date to end date.	Partially Missing Day: Set to last day of the month, unless the outcome is death in which case impute with min(last day of month, date of death) Month: December, unless the outcome is death in which case impute with min(DD-12-YYYY, date of death) Year: If the outcome is death then impute with the date of death, otherwise no imputation. Seconds: 59 Minutes: 59 Hours: 23 Completely Missing If the outcome is death then impute with the date of death, otherwise no imputation.

**STATISTICAL ANALYSIS PLAN
48-WEEK SAFETY FOLLOW-UP**

TITLE: A RANDOMIZED, DOUBLE-BLIND, DOUBLE DUMMY, ACTIVE-COMPARATOR MULTICENTER STUDY TO EVALUATE THE EFFICACY AND SAFETY OF RITUXIMAB VERSUS MYCOPHENOLATE MOFETIL IN PATIENTS WITH PEMPHIGUS VULGARIS

PROTOCOL NUMBER: WA29330

STUDY DRUG: Rituximab

VERSION NUMBER: 1

IND NUMBER: 121595

EUDRACT NUMBER: 2014-000382-41

SPONSOR: F. Hoffmann-La Roche Ltd.

PLAN PREPARED BY: [REDACTED], Ph.D.

DATE FINAL: See electronic date stamp below.

STATISTICAL ANALYSIS PLAN APPROVAL

Date and Time(UTC)	Reason for Signing	Name
18-Oct-2019 13:14:46	Company Signatory	[REDACTED]

CONFIDENTIAL

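### SAP 4.9.2 counts some adverse events that worsened and resolved before first dose as treatment-emergent, because its end-date check covers only events with an unknown start date

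*SAP*

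**What the plan says.** SAP 4.9.2 starts from onset date: "TEAEs are defined as those AEs with observed or imputed onset date on or after the start date of trial treatment". It then makes an exception for earlier onset, with two branches. The first compares grades: "Only where the most extreme intensity is greater than the initial intensity". The second needs no comparison and admits an event "or if most extreme intensity is not missing and initial intensity is missing". Neither branch refers to the date of worsening or to the end date.

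The next sentence does use an end date, but only for one kind of record: where the start is wholly unknown, the event counts unless a fully recorded end date places it before Day 1.

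The classification drives the summaries: "All AEs referenced in the section below will be TEAEs". A separate listing of screening events is planned, but nothing says that a listed event is kept out of the tables.

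Protocol 5.3.1 extends reporting before study drug beyond serious events caused by protocol-mandated procedures: "any adverse events occurring during any corticosteroid dose adjustment during the screening period should be reported". Protocol 5.3.5.4 asks sites for the initial and the most extreme intensity of a persistent event. It asks for a date when an event becomes serious, but not for a date when its grade rises.

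For an adverse-event start date with the month missing, SAP Appendix 11 has "Month: Set to max(01-01-YYYY, date of first treatment"). A closing note moves the imputed start back to the end date if it would otherwise fall after it.

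**The concern.** A treatment-emergent event should be one that began or got worse after treatment started. An event that rose in grade and ended during screening is neither, and no study drug can have caused it. The SAP's exception nevertheless admits it, because the rise in grade is tested without regard to when it happened.

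The outputs exposed are the adverse-event tables of SAP 4.9.2, including events by toxicity grade and corticosteroid-related events. The latter serve a stated safety objective (Protocol 2.2). If rates per 100 patient-years are produced, such an event would add to the numerator although it ended before any treatment exposure.

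**Working it through.** The plan gives no figure on this point to reproduce, so the check is to apply the text of SAP 4.9.2 to hypothetical events. Day 1 is first dose and G is grade. The last column applies the change proposed under the fix.

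| Case | Onset | Intensity | End | Literal rule | With end-date check |
|---|---|---|---|---|---|
| A | Day -20 | G1, G2 on Day -15 | Day -10 | counted | not counted |
| B | Day -20 | G1 throughout | Day -10 | not counted | not counted |
| C | Day -20 | initial missing, worst G1 | Day -10 | counted | not counted |
| D | Day -10 | G1, G3 on Day 20 | Day 30 | counted | counted |
| E | Day -20 | G1, G2 on Day -15 | Day 5 | counted | counted |
| F | unknown | G1, G2 on Day -15 | Day -10 | not counted | not counted |
| G | Day 3 | G1 throughout | Day 8 | counted | counted |

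1. Case A worsened and ended before treatment, yet the literal rule counts it.
2. Cases A and F differ only in whether the start date is known. The better-documented event is the one misclassified, so the two sentences of SAP 4.9.2 disagree about an event known to be over by Day 1.
3. Case C is admitted with no evidence of any worsening.
4. Case B shows the limit: a screening event whose grade did not change stays out.
5. Case E stays in after the fix. Removing it would need a date of worsening or a grade at Day 1, which Protocol 5.3.5.4 does not ask for.

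**Scale.** About 132 patients are randomized 1:1, so an arm has about 132 / 2 = 66. One misclassified patient is 1 / 66 = 1.5 percentage points of an arm. The documents give no screening event rate, so the number of such patients cannot be derived.

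**Direction.** Screening precedes randomization on Day 1 (Protocol 4.5.1.1), so each arm gains the same number in expectation. The expected difference in event counts is unchanged, and the ratio moves toward one.

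**Appendix 11.** Suppose the start year is recorded as Y, the month is missing and first treatment falls in year Y+1. The later of 1 January Y and first treatment is first treatment, so the imputed start leaves its recorded year and lands on Day 1. If the event has an end date before Day 1, the closing note pulls the start back. The misplacement survives only if the end date is missing or on or after Day 1. Screening lasts up to 28 days, so it also has to cross a year-end.

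**The case against.** The intent is visible. The exception is worded as a restriction, a screening listing is planned, and the following sentence shows that an event over by Day 1 was not meant to count. Sites are asked for two intensities and no date of worsening, so comparing the two and erring toward inclusion is an understandable default. Listings show all events, so affected records can be traced. This all stands and keeps the point minor. It does not remove it: the SAP states no further condition for a programmer to apply, and a listing does not take an event out of a table.

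A reader might infer more than the documents support:

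- **That screening steroid-taper events in general enter the tables.** Only those that worsened or lack an initial grade can do so. Collection is also limited: the screening taper is optional (Protocol 3.1.2), and a case like A must start, worsen and end within the screening period.
- **That a definite number of patients is affected.** Assuming that 10% to 30% of patients have a screening event and that 10% to 20% of those worsen and resolve before Day 1 gives 132 x 0.10 x 0.10 = 1.3 to 132 x 0.30 x 0.20 = 7.9 patients over both arms. Neither rate has any basis in the documents.
- **That one arm is favoured.** Pre-randomization events are balanced in expectation. Only chance imbalance remains.
- **That Appendix 11 has the same effect.** Its closing note prevents this for an event with an end date before Day 1, which is the case at issue here.

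**Conclusion.** The point holds as a small defect in a stated rule. Followed literally, SAP 4.9.2 counts screening events that worsened, or have no initial grade, and were over before first dose, and it treats a less well-documented event with the same end date the opposite way. The consequence is some inflation of treatment-emergent counts in both arms, with no expected advantage to either. Its frequency is unknown.

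The conclusion assumes that the rule is programmed as written and that sites report screening events as Protocol 5.3.1 requires. The Appendix 11 route is marginal. No efficacy analysis is affected.

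**What to change.** In SAP 4.9.2, extend the existing end-date check to every event with onset before treatment, for example: an adverse event with a complete, non-imputed end date before study Day 1 is not treatment-emergent, whatever its recorded intensities. This covers the missing-initial-intensity branch. Events ongoing at Day 1, or with a missing or partial end date, remain subject to the intensity test as a conservative default.

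The cost is one sentence, since SAP 4.9.2 and Appendix 11 already use end dates. The remaining weakness is case E: an event that worsened only before Day 1 and was still ongoing then is counted, because no date of worsening is requested.

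As a minor addition to Appendix 11, when the start month is missing and the recorded year is earlier than the year of first treatment, keep the imputed start within the recorded year.

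Section 1 of the 48-week safety follow-up SAP says that the primary analysis is complete. The practical step is therefore to confirm whether the program that flagged treatment-emergent events checked end dates against Day 1 and, if not, to list the records concerned.

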5.3.5.3 Adverse Events That Are Secondary to Other Events

In general, adverse events that are secondary to other events (e.g., cascade events or clinical sequelae) should be identified by their primary cause, with the exception of severe or serious secondary events. A medically significant secondary adverse event that is separated in time from the initiating event should be recorded as an independent event on the Adverse Event eCRF. For example:

- If vomiting results in mild dehydration with no additional treatment in a healthy adult, only vomiting should be reported on the eCRF.
- If vomiting results in severe dehydration, both events should be reported separately on the eCRF.
- If a severe gastrointestinal hemorrhage leads to renal failure, both events should be reported separately on the eCRF.
- If dizziness leads to a fall and consequent fracture, all three events should be reported separately on the eCRF.
- If neutropenia is accompanied by an infection, both events should be reported separately on the eCRF.

All adverse events should be recorded separately on the Adverse Event eCRF if it is unclear as to whether the events are associated.

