5.3.5.4 Persistent or Recurrent Adverse Events

A persistent adverse event is one that extends continuously, without resolution, between patient evaluation timepoints. The initial severity (intensity) of the event will be recorded at the time the event is first reported. If a persistent adverse event becomes more severe, the most extreme intensity should also be recorded on the Adverse Event eCRF. If the event becomes serious, it should be reported to the Sponsor immediately (i.e., no more than 24 hours after learning that the event became serious; see Section 5.4.2 for reporting instructions). The Adverse Event eCRF should be updated by changing the event from "non-serious" to "serious," providing the date that the event became serious, and completing all data fields related to serious adverse events.

A recurrent adverse event is one that resolves between patient evaluation timepoints and subsequently recurs. Each recurrence of an adverse event should be recorded as a separate event on the Adverse Event eCRF.

Rituximab—F. Hoffmann-La Roche Ltd
72/Protocol WA29330, Version 5

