4.7.2.2 Total Number of Flares

The total number of flares occurring during the treatment period will be evaluated by taking into account the number of flares experienced and the exposure period. Patient level flare and exposure data will then be aggregated, and the rate of flares compared between the RTX and MMF treatment groups. Rate of flare will be analyzed using a Poisson regression model with a log link and the log of each patient's duration in study as an offset variable. The model will include factors for treatment, region, duration of illness, baseline PDAI activity score, and baseline prednisone dose. The total number of flares, total exposure (weeks), and rate of flare will be presented by treatment group along with maximum likelihood estimates for the rate ratio, 95% confidence interval for the rate ratio, and p-value. A Pearson Chi-Square test will be used to assess over-dispersion of Poisson model. If an over-dispersion is detected based on this test, then a negative binomial model will be used. If the number of flares has an excess of zero counts according to the score test ([van den Broek, 1995](#)), a zero-inflated negative binomial model will be applied.

The exposure period for a patient will be the duration from Day 1 to the earliest of the following: early withdrawal, receipt of rescue, Week 52 visit.

Additional exploratory work may be undertaken to investigate the potential changes of flare rates over time, for example by assessing the number of flares over specified time intervals.

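### If the optional adverse-event rates per 100 patient-years are produced, their exact chi-square intervals ignore within-patient clustering and are too narrow for common, recurrent categories

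*SAP*

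**What the plan says.** SAP 4.9.2 makes the rates conditional and optional: "If an imbalance in exposure is found between treatment groups, AE rates per 100 patient-years exposure may be calculated". The formula that follows "AE rate per 100 patient-years is defined as" divides the number of events by total exposure and multiplies by 100. The numerator is therefore events, not patients with an event. On precision the section says only "The 95% CIs will be calculated based on exact X^2 distribution".

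The recording rules are in the protocol. Section 5.3.5.4: "Each recurrence of an adverse event should be recorded as a separate event on the Adverse Event eCRF". Section 5.3.5.3: "All adverse events should be recorded separately on the Adverse Event eCRF if it is unclear as to whether the events are associated".

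Neither SAP 4.9.2 nor the data-handling rules in SAP 4.10 give a patient-level variance, an over-dispersion check or a first-event rate for adverse events. SAP 4.7.2.2 does plan a check for disease flares: "A Pearson Chi-Square test will be used to assess over-dispersion of Poisson model", followed by "If an over-dispersion is detected based on this test, then a negative binomial model will be used".

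**The concern.** An exact chi-square interval for a rate is valid when the event total behaves as a Poisson count, with variance equal to its mean. That fails when patients differ in their underlying rates or when one event makes another more likely in the same patient.

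The protocol gives reason to expect differing rates. Under the guideline in Protocol 3.1.2 (Table 1), prednisone can lie anywhere from 0 to 240 mg/day, and Protocol 5.1.3 links corticosteroids to infection risk. Each patient is also scheduled for up to four infusions, so infusion reactions can repeat.

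These rates are the only exposure-adjusted adverse-event summary in SAP 4.9.2. Safety data stop at rescue (SAP 4.9), so arms with different failure rates could well differ in exposure, which is the condition for producing the rates. A reader who sets the two arms' intervals side by side would then see more precision than the data hold, for example for infections.

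**Working it through.** **Inputs from the documents.** About 132 patients randomized 1:1 (SAP 2.3), so 132 / 2 = 66 per arm. Telemedicine patients are left out of the mITT population, not the safety population. The treatment period is 52 weeks, taken as 1 patient-year each. Nominal level 95% (SAP 4.9.2).

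**Assumed inputs.** The documents state no event mean or dispersion. Let m be the mean number of events per patient, from 0.1 to 5. Let k be the negative-binomial dispersion, from 10 (mild clustering) to 0.5 (strong). Patients are treated as a sample whose individual rates vary.

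**Planned interval.** For x events the limits are chi2(0.025; 2x)/2 and chi2(0.975; 2x+2)/2, each divided by exposure.

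**Clustered counts.** Variance per patient is m + m²/k, so the variance of the total is inflated by 1 + m/k. A correct interval is about sqrt(1 + m/k) times as wide.

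**Coverage.** The total over 66 patients is negative binomial with mean 66m and dispersion 66k. Coverage is the probability that this total gives a planned interval containing 66m. The no-clustering column reproduces the SAP's nominal level (slightly conservative at small counts).

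| m | No clustering | k=10 | k=5 | k=2 | k=1 | k=0.5 |
|---|---|---|---|---|---|---|
| 0.1 | 97.2% | 97.1% | 97.0% | 96.8% | 96.4% | 95.6% |
| 0.3 | 95.7% | 95.4% | 95.1% | 94.1% | 92.4% | 89.1% |
| 1 | 95.1% | 94.0% | 92.8% | 89.3% | 83.7% | 74.6% |
| 3 | 95.3% | 91.9% | 88.5% | 79.2% | 68.1% | 54.8% |
| 5 | 95.3% | 89.4% | 83.9% | 71.1% | 58.2% | 45.0% |

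**Width factors.**
- m=1: sqrt(1 + 1/10) = 1.05 at k=10; sqrt(1 + 1/0.5) = 1.73 at k=0.5.
- m=5: sqrt(1 + 5/10) = 1.22 at k=10; sqrt(1 + 5/0.5) = 3.32 at k=0.5.
- m=0.1: at most sqrt(1 + 0.1/0.5) = 1.10.

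**Example.** At m=3, 66 × 3 = 198 events in 66 patient-years, or 300 per 100 patient-years. The planned interval is 260 to 345. Allowing for clustering, the log-scale standard error is sqrt((1 + 3/k)/198) and the interval is 300 × exp(±1.96 × SE):
- k=10: SE 0.081, 256 to 352
- k=1: SE 0.142, 227 to 396
- k=0.5: SE 0.188, 208 to 434

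**The case against.** The strongest reply is that little depends on this output. The SAP says the rates may be calculated, and only if exposure is imbalanced. No adverse-event test, rate ratio, rate difference or similarity margin is planned, and SAP 4.7 limits formal testing to the primary and five ranked secondary endpoints. Patient counts and percentages by system organ class and preferred term are planned anyway, and within-patient clustering does not affect those. All of this stands and limits the consequence. It does not make the interval correct when used, and the patient counts do not adjust for exposure.

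The size is assumed. If clustering is mild, the shortfall at 1 event per patient is about one point. Several recording rules also curb repeat counting: a persistent event is one event (Protocol 5.3.5.4), secondary events generally go under their primary cause (5.3.5.3), a diagnosis replaces its signs and symptoms (5.3.5.2), and the same laboratory abnormality is not re-entered at each visit (5.3.5.5). These argue for the milder end of the range but do not remove true recurrences.

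Three stronger readings are tempting and should be resisted:
- A reader might infer that every adverse-event interval is too narrow. At 0.1 events per patient, coverage stays at 95.6% or above for every k tried, and events such as those leading to death or withdrawal cannot cluster within a patient.
- A reader might infer that the plan could produce a false formal safety finding. No test is attached, and each interval describes one arm.
- A reader might see the flare analysis as proof of inconsistency. Flare count is second in the confirmatory sequence and yields a p-value, which is reason enough for its extra safeguard. It shows that the SAP has a suitable method to hand, not that it contradicts itself.

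**Conclusion.** The point holds for common, recurrent categories: all AEs, infections, and possibly corticosteroid-related AEs and infusion reactions. If the rates are produced as written, those 95% intervals will be too narrow. Under assumed means of 1 to 5 events per patient with 66 patients per arm, coverage is about 94% to 89% with mild clustering (k=10) and 75% to 45% with strong clustering (k=0.5). At 0.3 events per patient the loss ranges from nil to about six points. For rare and at-most-once categories the exact interval is adequate.

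Confidence is high for the direction and low for the size, because means and dispersions are assumptions; with no clustering there is no shortfall. The widening by a factor of 3.32 is the most extreme combination tried, not a typical value. Reading the exact chi-square interval as the Poisson interval is the standard interpretation, although SAP 4.9.2 does not use that word. Efficacy conclusions and type I error are untouched. It is worth correcting because a pre-specified method would misstate precision and the correction is cheap.

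**What to change.** Amend SAP 4.9.2 so that the interval depends on the category, with the categories named in advance:

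- **Common recurrent categories** (all AEs, infections and, if frequent, corticosteroid-related AEs and infusion reactions): keep the event rate, but compute its 95% interval with the patient as the unit, using a robust or negative-binomial variance or a patient-level bootstrap.
- **Rare categories** (about 0.1 events per patient or fewer) **and events that occur at most once per patient**: keep the exact chi-square interval. With few or no events a bootstrap can collapse and a negative-binomial fit can be unstable, so a blanket replacement could make these worse.
- **Optional addition:** patients with a first event divided by time to first event, with the exact interval, labelled as a different quantity from the event rate.

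The cost is a few lines of SAP text, minor programming and wider intervals for the common categories. No new data and no change to trial conduct are needed.
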